23 24 **IV. MATERIALS AND SUPPLIES**

25 26 **A. Study Drugs**

27
28 Intravenous ceftriaxone at a dose of 2 grams daily or intravenous placebo (dextrose) will
29 be administered for the first 30 days of the treatment period to patients assigned to the
30 active treatment group (Group A) and the placebo treatment group (Group B)

1 respectively. Patients in group A will then receive doxycycline 100 mg every 12 hours
2 orally for 60 consecutive days and patients in group B will receive an identical placebo
3 every 12 hours orally for 60 consecutive days. [name] or a physician co-
4 investigator of New England Medical Center and [name] or a physician co-
5 investigator of New York Medical College, will supervise all aspects of the
6 administration of the study medications. Patients will receive intravenous therapy at
7 home with an indwelling short plastic venous access catheter.

8 There will be two groups in this study with 97 patients in each group:

- 9
- 10 1. IV ceftriaxone x 30 days followed by oral doxycycline x 60 days
 - 11
 - 12 2. IV placebo (dextrose) x 30 days followed by oral placebo (dextrose) x 60 days
 - 13

14 **V. PATIENT SELECTION AND ENROLLMENT**

15

16 **A. Study Population**

17

18 This study will be conducted in 194 patients with CLD. Enrollment will begin in
19 approximately April 1997 and proceed until the quota of patients is reached. We
20 anticipate an enrollment period not to exceed three years.

21

22 **B. Inclusion and Exclusion Criteria**

23

24 For the double-blind, placebo-controlled trial of antibiotics vs. placebo in seropositive
25 patients with chronic Lyme disease, the following criteria for inclusion will be used.

26

1 Inclusion criteria:

2 1. IgG seropositivity at the time of enrollment into the study for an immune response
3 to *B. burgdorferi* antigens according to the currently accepted CDC (Dearborn)
4 criteria defined in reference ¹³ .

5 2. 18 years of age or older.

6 3. Able to give informed consent.

7 4. Physician documented history of prior antibiotic treatment with a currently
8 recommended antibiotic regimen that was appropriate for the patient's clinical
9 features of Lyme disease at the time of presentation (table on page 8 of the
10 technical proposal).

11 5. A past history of one or more of the following clinical features typical of Lyme
12 disease acquired in the United States:

13 a) A past history of erythema migrans defined as an erythematous skin lesion

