27 will be scored as improved if they are better on both scales or better on one scale and are
28 not worse on the other scale.

1 The primary analysis will be an intent-to-treat analysis of all patients enrolled in the
2 study. For secondary analysis, patients will be evaluated who have received at least 75%
3 of the course of study therapy. Both analyses will involve comparisons between the
4 proportion of patients improved at 6 months in the placebo and treated groups. A
5 secondary analysis will compare the groups at the end of parenteral (30 days) and total
6 active treatment (90 days). Comparison will consist of a χ^2 test at a significance level of
7 0.05, together with an estimate of treatment efficacy (risk ratio and risk difference) with
8 95% confidence intervals. As secondary and exploratory analyses, we will check to see if
9 efficacy differs across subgroups by examining interaction terms in a multivariate
10 analysis. We will also determine whether changes in patient performance on the
11 supplementary MOS scales correlate with changes in the SF-36. Such subgroup analyses
12 will need further confirmation in future studies. Nevertheless, their discovery may
13 suggest important treatment interactions.

14
15 Tests will be done to ensure that no important potential confounders are unevenly
16 distributed between patient groups. Regression analysis will be performed to determine
17 the effect on results if any confounders are identified. An analysis stratified by duration
18 of symptoms of chronic Lyme disease will be performed. An analysis stratified by site
19 also will be performed to ensure that the results are not dependent on site. Among
20 potential confounders and interaction variables are demographic variables (e.g., age, sex,
21 race, education and location), medical history variables (e.g., previous psychiatric illness,
22 prior history of arthralgia or arthritis, duration of symptoms, and interval between onset
23 of acute Lyme disease and chronic symptoms) and physical examination variables (e.g.,
24 tender points and findings on neurologic examination).

25 26 C. Statistical Analysis

27 28 Study Sample Size

1 For a long course of high dose antibiotics to show efficacy there should be a substantial,
2 durable difference between the antibiotic treated and the placebo groups. We shall
3 assume that the natural healing rate is 0.40 or 40%. For an efficacy study in which the

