4 placebo rate is 0.4 and the expected treated rate is 0.65, we need a total of 124 (62
5 patients per group) to attain 80% power at a 0.05 (two-sided) level³¹. Dividing by 0.85 to
6 allow for 15% dropouts gives a total of 146 patients. To achieve a 90% power, requires
7 194 patients with the same assumptions. The latter corresponds to an analysis with a 95%
8 confidence interval half width of approximately 0.15. The sample size of 194 is also
9 sufficient to allow us to rule out, at a one sided 0.025 level, a benefit of treatment as high
10 as 0.25 in the healing rate, if the true healing rates are 0.4 for both the antibiotic treatment
11 and placebo³².

12
13 As an interim analysis it is appropriate to consider performing the study on seropositive
14 patients with a sample size designed to show whether antibiotic treatment is equivalent to
15 placebo treatment (a trial of equivalency). To determine the sample size necessary to
16 show this, we need to define what "not effective treatment" means and to define the
17 proportion of cases that would improve naturally without treatment or would improve by
18 placebo treatment. We define treatment as ineffective if we can be reasonably sure (95%)
19 that the difference between the healing rate under treatment (pE) and the natural healing
20 rate (pS) is no greater than a defined magnitude (d). This is equivalent to showing that
21 there is a high probability that the upper bound on a confidence interval for $|pE - pS|$) is
22 less than d. (R. Makuch and R. Simon, Cancer Treatment Reports 62: 1037-1040, 1978).
23 We shall assume that the natural healing rate is 0.10 or 10%. Then in order to have a
24 minimum of 5 expected events (i.e. improvement) in the placebo group, we need a
25 sample size of 50 in the placebo group. Assuming that the rate of improvement in the
26 antibiotic treated group is the same as in the placebo treated group ($pE = pS$) and that
27 there are 50 patients in each group, there is a 99% chance that we will be able to exclude
28 any treatment difference greater than 25% using a 95% confidence interval (i.e., the
29 power is 0.99 for $d=0.25$ and $\alpha=0.05$). This sample size also gives 95% power for
30 detecting a 20% treatment efficacy ($d=0.20$) and power = 0.80 for 15% ($d=0.15$). By

1 assuming a drop-out rate of 10% from each group a sample size of 55 patients in each
2 group, or a total of 110 patients, would be required to be enrolled at the time of interim
3 analysis.

4

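### The interim power figures assume a 10% natural healing rate and the main sample size assumes 40% for the same patients, with no reason given for the difference

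*Protocol*

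**What the plan says.** All the relevant text is in Protocol Section VIII.C, under Study Sample Size.

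The first paragraph sizes the trial. The investigators "assume that the natural healing rate is 0.40 or 40" per cent and continue: "placebo rate is 0.4 and the expected treated rate is 0.65, we need a total of 124 (62" per group) for 80% power. With 15% dropout this becomes 146 patients, and 90% power is said to need 194. The same paragraph adds a rule-out statement for the full sample at a one-sided 0.025 level. With 194 patients the trial can exclude a benefit as high "as 0.25 in the healing rate, if the true healing rates are 0.4 for both the antibiotic treatment" and placebo.

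The second paragraph turns to an interim trial of equivalency: "As an interim analysis it is appropriate to consider performing the study on seropositive" patients. Here the rate changes: "We shall assume that the natural healing rate is 0.10 or 10" per cent. Two things are derived from it:

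- 50 patients per group, chosen so that the placebo group has at least 5 expected improvements;
- powers of 0.99, 0.95 and 0.80 to exclude differences of 0.25, 0.20 and 0.15 when the two true rates are equal.

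Allowing 10% dropout, 110 patients are to be enrolled by the interim.

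The interim population is the trial population. Section V.B introduces its inclusion criteria with "For the double-blind, placebo-controlled trial of antibiotics vs. placebo in seropositive" patients.

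**The concern.** One named quantity has two values in adjacent paragraphs. The interim paragraph explains the rate as the proportion who would improve untreated or on placebo, and it counts improvements as its events. Section VIII.B uses improvement as the primary outcome. No separate endpoint, time point or subgroup is given for the interim.

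The type of analysis does not explain the difference either. The full-sample rule-out asks the same kind of question, whether a given benefit can be excluded when the arms are truly equal, and it uses 0.4 in both arms. Nor is 0.10 the cautious choice for such an analysis: a rate further from one half has a smaller variance, so it flatters the power.

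What is at stake is how an inconclusive interim is read. If 0.40 is right, an interim that fails to exclude a difference of 0.20 or 0.15 is far more likely under truly equal arms than the stated powers suggest.

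**Working it through.** **Inputs**, all from Protocol Section VIII.C: n = 50 evaluable per group; equal true rates p in both arms; margins d = 0.25, 0.20, 0.15; alpha 0.05, sidedness not stated; p = 0.10 (interim) or 0.40 (main design). The 97 patients per group in the whole trial come from Section IV.A.

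**Formula.** The difference is excluded when the upper confidence bound lies below d. With unpooled variance,

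power = Φ(d / SE − z), SE = √(2p(1−p)/n).

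**Step 1: reproduce the stated figures.** At p = 0.10, SE = √(2 × 0.09/50) = 0.060. With z = 1.645 (one-sided 5%):

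- d = 0.25: Φ(4.167 − 1.645) = 0.994
- d = 0.20: Φ(3.333 − 1.645) = 0.954
- d = 0.15: Φ(2.500 − 1.645) = 0.804

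These match the stated 0.99, 0.95 and 0.80. Exact binomial enumeration of the same bound gives 0.992, 0.948 and 0.806. Other conventions do not match all three at p = 0.10: one-sided 0.025 gives 0.986, 0.915 and 0.705, and a two-sided equivalence criterion at 0.05 gives 0.988, 0.909 and 0.607. The protocol's figures therefore imply a one-sided 5% bound, although its text speaks of a 95% interval and of the absolute difference.

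**Step 2: change only the rate.** At p = 0.40, SE = √(2 × 0.24/50) = 0.098. The variance is 0.24/0.09 = 2.67 times as large.

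| d | Stated | p = 0.40, z = 1.645 | p = 0.40, z = 1.96 |
|---|---|---|---|
| 0.25 | 0.99 | Φ(2.552 − 1.645) = 0.818 | 0.723 |
| 0.20 | 0.95 | Φ(2.041 − 1.645) = 0.654 | 0.532 |
| 0.15 | 0.80 | Φ(1.531 − 1.645) = 0.455 | 0.334 |

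Exact enumeration at p = 0.40 gives 0.822, 0.652 and 0.460 at one-sided 5%, and 0.719, 0.542 and 0.326 at one-sided 0.025.

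**Step 3: patients needed to keep the stated powers at 0.40.** n per group = 2p(1−p)(z + z_power)²/d², with z = 1.645:

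- d = 0.25, power 0.99: 0.48 × (1.645 + 2.326)²/0.0625 = 121.1, so 122
- d = 0.20, power 0.95: 0.48 × (1.645 + 1.645)²/0.04 = 129.9, so 130
- d = 0.15, power 0.80: 0.48 × (1.645 + 0.842)²/0.0225 = 131.9, so 132

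Each exceeds the 97 per group in the whole trial, so the stated powers cannot be recovered at 0.40 by moving the interim later.

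**Step 4: the basis for 50 per group.** Five expected placebo improvements need 5/0.10 = 50 patients at the interim rate, but only 5/0.40 = 12.5 at the main rate. At 0.40 that criterion no longer leads to 50.

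**Step 5: the main design.** Rates of 0.40 and 0.65 give 62 per group at 80% power, and 124/0.85 = 146, as stated. At 90% power they give 82 per group, and 164/0.85 = 193, against the stated 194. The main calculation holds together at 0.40.

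**The case against.** The strongest defence is that nothing central depends on the interim paragraph. The 194-patient size and the full-sample rule-out use 0.40, and the primary six-month χ² comparison does not draw on the interim figures. The interim powers are correct for the rate they state. This stands: the fault is an inconsistent assumption, not a miscalculation, and it does not unsettle the main design.

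The document also does not show which rate is true. This stands too. The fall in power is conditional on 0.40. If 0.10 were right, the interim powers would hold under their one-sided 5% convention, and the main calculation would need redoing.

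Three stronger readings are tempting, and the text does not carry them:

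- A reader might infer that the interim is badly underpowered for every listed margin. At one-sided 5% the power for 0.25 is still about 0.82, above the 80% that the protocol uses as its first target, and 0.25 is the only margin in the full-sample rule-out. Only at one-sided 0.025 does it drop to 0.72.
- A reader might infer that the monitoring board would judge the interim against the stated powers. The paragraph does not say who reviews the interim or what follows from it. The board or its safety officer appears for adverse-event reports (Section VII.A), laboratory data (Section VIII.C, Safety Evaluations) and case report forms (Section IX).
- A reader might take the three margins as decision rules and conclude that 0.20 and 0.15 must go. The paragraph sets no stopping rule. It leads with 0.25 and adds power for the other two.

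**Conclusion.** The inconsistency is real, and no passage in the protocol resolves it. The stated interim powers of 0.99, 0.95 and 0.80 do not hold under the rate that justifies the trial's size. At 0.40 and 50 evaluable per group, with truly equal arms, they would be about 0.82, 0.65 and 0.45 with the one-sided 5% bound that the protocol's figures imply. At one-sided 0.025 they would be about 0.72, 0.53 and 0.33. At one-sided 5%, the chance of failing to exclude the margin would be about 18% rather than 1% for 0.25, 35% rather than 5% for 0.20, and 54% or 55% rather than 20% for 0.15.

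The interim therefore remains usable for 0.25 and is weak for the two smaller margins. This rests on 0.40 being the intended rate and on the normal approximation, which exact enumeration supports. It should be corrected before any interim look, but it is not a defect in the main design.

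**What to change.** In Section VIII.C:

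1. Use one natural healing rate throughout, or state why two are needed. The default is 0.40, because the enrolled size and the full-sample rule-out rest on it. If 0.10 is intended, redo the 194-patient calculation and the rule-out statement instead.
2. State the confidence level of the interim bound and whether the criterion is one-sided or two-sided. The full-sample rule-out uses one-sided 0.025, while the interim figures imply one-sided 0.05.
3. Restate the interim powers at the chosen rate and level. At 0.40 and 50 per group these are about 0.82, 0.65 and 0.45 (one-sided 0.05) or 0.72, 0.53 and 0.33 (one-sided 0.025).
4. Replace the five-expected-events argument for 50 per group, since at 0.40 it no longer gives that number.

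The margins of 0.20 and 0.15 can stay if their actual power is printed beside them. At 0.40 the cost is protocol wording and less favourable interim figures. No patients are added.

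### The interim equivalence powers fit a one-sided 5% bound on the signed difference, not the stated 95% interval on the absolute difference, and one of them is described as power to detect

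*Protocol*

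**What the plan says.** All the text is in Protocol section VIII.C, Study Sample Size.

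- **Interim rule.** Treatment counts as ineffective if one can be 95% sure that its healing rate does not differ from the natural rate by more than d. This is restated as showing that "there is a high probability that the upper bound on a confidence interval for" the absolute difference |pE - pS| is less than d.
- **Interim inputs.** "We shall assume that the natural healing rate is 0.10 or 10"%. The two rates are taken as equal, with 50 patients per group.
- **Interim claim.** There is a 99% chance of excluding "any treatment difference greater than 25% using a 95% confidence interval (i.e., the" power being 0.99 for d=0.25 at alpha=0.05. The same sample is said to give 95% power for "detecting a 20% treatment efficacy" (d=0.20) and power 0.80 for d=0.15. The paragraph does not say whether the interval or the alpha is one- or two-sided.
- **Final rule-out.** The preceding paragraph says that 194 patients are "sufficient to allow us to rule out, at a one sided 0.025 level, a benefit of treatment as high" as 0.25, if both true rates are 0.4. It also gives a 95% confidence interval half width of about 0.15 for that sample.

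**The concern.** A rule and its powers should describe the same test. Here the rule is on the absolute difference with a 95% interval, while the powers appear to come from a one-sided 5% bound on the signed difference.

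The choice matters because this rule is the one by which an early look would call the antibiotic regimen ineffective. On one reading the interim is less likely to reach that conclusion correctly than the protocol says. On the other, it may reach it at a looser level than the final analysis applies to the same 0.25 margin.

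Separately, a reader who takes the word detecting at face value would think the interim has a 95% chance of finding a true 20-point benefit.

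**Working it through.** **Inputs (section VIII.C):** pE = pS = 0.10; n = 50 per group; d = 0.25, 0.20, 0.15; 95% interval, alpha = 0.05.

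**Standard error:** SE = sqrt(2 × 0.10 × 0.90 / 50) = 0.06, so d/SE = 4.167, 3.333, 2.500.

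**Formulas (normal approximation, true difference zero):**
- signed difference, upper bound below d: power = Φ(d/SE − z)
- absolute difference, interval within ±d: power = 2Φ(d/SE − z) − 1

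**Step 1: reproduce the stated figures.** With z = 1.645 on the signed difference: Φ(2.522) = 0.994, Φ(1.688) = 0.954, Φ(0.855) = 0.804. These match 0.99, 0.95 and 0.80.

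**Step 2: the other readings.**

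| Criterion | d=0.25 | d=0.20 | d=0.15 |
|---|---|---|---|
| Stated in the protocol | 0.99 | 0.95 | 0.80 |
| Signed, one-sided 5% (z=1.645) | 0.994 | 0.954 | 0.804 |
| Signed, upper limit of two-sided 95% CI (z=1.96) | 0.986 | 0.915 | 0.705 |
| Absolute, z=1.645 | 0.988 | 0.909 | 0.608 |
| Absolute, z=1.96 | 0.973 | 0.830 | 0.411 |

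Exact binomial enumeration of the signed rule gives 0.992/0.948/0.806 at z = 1.645 and 0.983/0.917/0.716 at z = 1.96, so the approximation does not drive the result. A continuity-corrected one-sided 5% bound gives 0.981/0.912/0.712, and a Farrington-Manning variance gives 0.986/0.922/0.746. Of the variants tried, only the uncorrected one-sided 5% bound on the signed difference yields all three stated figures. The absolute-value rule misses 0.95 and 0.80 at either z.

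**Step 3: what a 95% interval means in the preceding paragraph.** With 15% dropout, 97 × 0.85 ≈ 82 evaluable per group. At 0.40 vs 0.65, SE = sqrt((0.24 + 0.2275)/82) = 0.0755, and 1.96 × SE = 0.148. At 0.40 vs 0.40, SE = 0.0765, and 1.96 × SE = 0.150. With 1.645 the half widths would be 0.124 and 0.126. The stated half width of about 0.15 is therefore two-sided.

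**Step 4: level if the interim bound is one-sided.** With a true benefit equal to d, a one-sided 5% bound wrongly excludes it with nominal probability 0.05, against 0.025 for the final rule-out. Exact enumeration at 10% vs 35%, n = 50, gives 5.1% with z = 1.645 and 2.8% with z = 1.96.

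**Step 5: power to detect.** For 10% vs 30%, n = 50, two-sided 0.05: the pooled SE is sqrt(2 × 0.20 × 0.80 / 50) = 0.080, and the unpooled SE is sqrt((0.09 + 0.21)/50) = 0.0775. Power = Φ((0.20 − 1.96 × 0.080)/0.0775) = Φ(0.558) = 0.71, not 0.95.

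**Step 6: dependence on the 10% rate.** The final design assumes 40%. At 40% in both arms, SE = sqrt(2 × 0.24 / 50) = 0.098, and the one-sided 5% powers fall to 0.82/0.65/0.45.

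**The case against.** The strongest reply is that nothing has been miscalculated. The rule speaks of being 95% sure and of an upper bound, and its question is whether treatment is better by more than d. The interim paragraph never says two-sided, although the paragraph before it states sidedness where it uses a significance level. Read as a one-sided 95% bound, all three powers are correct. This stands: a reader might infer an arithmetic error, and the documents do not establish one. What the reply leaves unexplained is the absolute-value sign, which fits the d=0.20 and d=0.15 powers at neither z, and the two-sided use of a 95% confidence interval one paragraph earlier. The expression does have an unmatched parenthesis and may be garbled, so the figures 0.830 and 0.411 should be taken as the rule as printed and not as the probable intention.

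A reader might also infer that the interim is both overpowered on paper and looser than the final analysis. The documents do not support the two together. A two-sided interval aligns the levels and makes two powers too high; a one-sided bound makes the powers right and the level looser.

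Three further points limit the weight:
- At d=0.25, the margin shared with the final rule-out, the signed power changes only from 0.99 to 0.986.
- The final rule-out at one-sided 0.025 is a sample-size statement. The primary analysis is a chi-squared test at 0.05 with 95% intervals.
- The interim text is tentative and states no stopping action. A looser exclusion level there raises the risk of missing a benefit, not of falsely claiming one.

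Finally, the sentence before the word detecting assumes equal rates and speaks of exclusion, so a careful reader can recover the meaning. The sentence is still wrong as written.

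**Conclusion.** The point holds as an inconsistency between the stated rule and the stated powers. One of two things is true:

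- A two-sided 95% interval is meant. Power on the signed difference is then overstated by 3.5 points at d=0.20 (0.95 vs 0.915) and 9.5 points at d=0.15 (0.80 vs 0.705), with almost no change at d=0.25. On the absolute difference as printed, the powers are 0.973/0.830/0.411.
- A one-sided 95% bound is meant. The powers are then right only without the absolute value, and the interim level for excluding a 0.25 benefit is 0.05, twice the 0.025 of the final rule-out.

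The documents do not settle which. Under both, the 95% attached to d=0.20 is a probability of exclusion under equal rates; power to detect 10% vs 30% with 50 per group is about 0.71.

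These results rest on the protocol's 10% rate, 50 evaluable per group and the normal approximation, which exact enumeration supports. The 0.71 assumes a two-sided 0.05 superiority test, which the interim paragraph does not itself propose; it serves only to show what the word detecting would imply. The 10% assumption matters more than sidedness: at the 40% used for the final design, even the one-sided 5% powers are 0.82/0.65/0.45.

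**What to change.** In the interim paragraph of section VIII.C:

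1. State one criterion: the upper limit of the two-sided 95% confidence interval for pE - pS (one-sided 0.025, as for the final rule-out) lies below a named d.
2. Remove the absolute-value sign.
3. Restate the powers as 0.986, 0.915 and 0.705 for d = 0.25, 0.20 and 0.15, labelled as conditional on a 10% rate in both arms, since the final design assumes 40%.
4. Replace "detecting a 20% treatment efficacy" with wording about excluding a 20-point difference when the true rates are equal.

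If the sponsor prefers a one-sided 5% bound, the present powers can stay. The text should then say that the bound is one-sided, drop the absolute value, and state that the interim level is looser than the final one.

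The cost is protocol wording and, under the first option, less favourable interim figures. Keeping 0.99, 0.95 and 0.80 with the two-sided interval would need 53, 59 and 63 evaluable patients per group respectively, against the stated 50.

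### The interim enrolment of 110 allows 10% dropout, while the main sample size in the same section allows 15%; no reason is given, and the inflation method differs (minor)

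*Protocol*

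**What the plan says.** Both calculations stand in Protocol section VIII.C, Study Sample Size.

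- **Main calculation.** With improvement rates of 0.40 and 0.65, it needs 62 patients per group (124 in total) for 80% power at a two-sided 0.05 level. It divides by 0.85 to "allow for 15% dropouts gives a total of 146 patients". The 194 for 90% power is said to rest on the same assumptions.
- **Interim calculation.** The text asks the reader to "assume that the natural healing rate is 0.10 or 10"%. To have a "minimum of 5 expected events (i.e. improvement) in the placebo group, we need a" "sample size of 50 in the placebo group". It then states that, with equal true rates and if "there are 50 patients in each group, there is a 99% chance that we will be able to exclude" a difference above 25%. Powers of 0.95 and 0.80 follow for margins of 20% and 15%.
- **Interim dropout.** The last sentence reads "assuming a drop-out rate of 10% from each group a sample size of 55 patients in each" "group, or a total of 110 patients, would be required to be enrolled at the time of interim" analysis.

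The section gives no reason for using a different dropout allowance at the interim.

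**The concern.** The interim is a look at the same seropositive cohort, yet one section plans for two attrition rates and inflates for them in two ways. The 110 is the only enrolment figure that the protocol attaches to the interim. The 50 per group behind it has an explicit basis: a floor of five expected placebo events, and powers quoted for exactly that number. If the main allowance of 15% is the realistic one, 110 enrolled patients would not deliver the 50 per group on which that floor and those powers rest.

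**Working it through.** **Inputs, all from section VIII.C.** Main: rates 0.40 and 0.65, two-sided 0.05, 80% and 90% power, dropout 15%. Interim: 50 per group, healing rate 0.10 in both groups, at least 5 expected placebo events, dropout 10%, 55 per group enrolled.

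**1. Reproduce the main figures.** The usual two-proportion formula without continuity correction gives 62 per group at 80% power and 82 at 90%.
- 80%: 62/0.85 = 72.9, so 73 per group and 146 in total, as printed.
- 90%: 82/0.85 = 96.5, so 97 per group and 194 in total, as printed.

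The protocol's working rule is therefore n/(1 − dropout), rounded up.

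**2. Reproduce the interim figure.** 50 × 1.10 = 55, as printed. The main rule gives 50/0.90 = 55.6, so 56 per group and 112 in total. Rounding 55.6 down would also give 55. Either way the difference is one patient per group.

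**3. The same rule at the main 15%.** 50/0.85 = 58.8, so 59 per group and 118 in total, which is 8 more than 110.

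**4. What each enrolment leaves per group.** Expected events are patients left × 0.10.

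| Enrolled per group | Dropout | Patients left | Expected placebo events |
|---|---|---|---|
| 55 | 10% | 49.5 | 4.95 |
| 55 | 15% | 46.75 | 4.68 |
| 56 | 10% | 50.4 | 5.04 |
| 59 | 15% | 50.15 | 5.02 |

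**5. Effect on the printed powers.** Power = Φ(d/√(2 × 0.10 × 0.90/n) − 1.645). The critical value 1.645 is used because it reproduces the printed values.

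| n per group | d = 0.25 | d = 0.20 | d = 0.15 |
|---|---|---|---|
| 50 (printed 0.99/0.95/0.80) | 0.994 | 0.954 | 0.804 |
| 49.5 | 0.994 | 0.953 | 0.800 |
| 46.75 | 0.991 | 0.943 | 0.780 |

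The largest loss is 0.804 − 0.780 = 0.024, at d = 0.15 and 15% dropout.

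**6. Dependence on the healing rate.** The main calculation assumes a natural healing rate of 0.40. At that rate 46.75 placebo patients give 46.75 × 0.40 = 18.7 expected events, and the five-event floor is met easily. The powers change far more: with n = 50, d = 0.25 and the same critical value, power is 0.82 instead of 0.99.

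**The case against.** The case for leaving the text alone has four parts.

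- **Rounding.** At the stated 10%, the gap is half a patient and 0.05 of an event per group. The number of dropouts among 55 patients has a standard deviation of √(55 × 0.10 × 0.90) = 2.2, over four times the gap. This stands. A reader might infer that 110 fails its requirement under either dropout rate, but at 10% that would treat rounding as a failure.
- **Planning allowances.** A reader might also infer that one of the two rates must be wrong, or that 118 is the correct number. The protocol does not support this. It contains no dropout data, and 15% may simply be the more cautious allowance. What stands against the text is that the difference is unexplained.
- **Endpoint and analysis set.** The interim paragraph names no time point, and section VIII.B makes the primary analysis intent-to-treat on all enrolled patients. How many patients dropout removes from the interim comparison therefore cannot be read directly from the rate. But the protocol itself inflates for dropout in both calculations, so it counts dropouts as lost in both.
- **Consequence.** The interim text gives no boundary that turns on 46.75 against 50, and the power loss is at most 2.4 percentage points. This stands, and it keeps the point minor. The inconsistency still concerns two figures printed in the protocol, so it is not a detail left to a statistical analysis plan.

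**Conclusion.** The point holds as a minor inconsistency. Section VIII.C uses 15% and division for the main sample size, but an unexplained 10% and, in effect, multiplication by 1.10 for the interim. By the protocol's own rule, 50 per group needs 112 enrolled at 10% or 118 at 15%, against the printed 110.

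The shortfall is noticeable only if 15% also applies at the interim: about 3 patients per group (50 − 46.75 = 3.25), 4.7 expected events instead of 5, and powers of about 0.99/0.94/0.78. The event shortfall further assumes the interim's 10% healing rate and disappears at the main 40%. That conflict between healing rates matters more than the dropout inputs, and it decides whether 50 per group is the right starting number at all.

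**What to change.** Change the last sentence of the interim paragraph in section VIII.C in one of two ways:

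- apply the main 15% and divide by 0.85, giving 59 per group and 118 in total; or
- keep 10%, state why fewer dropouts are expected at the interim, and divide by 0.90, giving 56 per group and 112 in total.

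First reconcile the 10% and 40% healing rates. If the 50 per group changes, apply the chosen dropout rate and the division to the new number; 56 and 59 hold only for a base of 50.

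The cost is one sentence. No extra patients are needed and the total of 194 is unchanged. With a base of 50, the interim falls 2 patients later at 10% or 8 later at 15% (8/194, about 4% of enrolment).
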